The secondary objective is to compare the primary and secondary outcomes when stratified by stone size. This will allow us to explore the efficiency between Moses and thulium laser on treating large vs. small stones. Previous literature suggested that stone size was associated with operative time.^{ix} Patients will be separated based on the size of their stones: 3-10 mm or 11-20 mm and then randomized to holmium laser with Moses or thulium laser. Patients will be randomized into the groups by a ratio of 1:1.

Research Design and Methods

This study will be a randomized trial comparing ureteroscopy with laser lithotripsy with the Lumenis® Pulse™ P120H holmium laser system with the Moses technology (holmium laser with moses) versus the Soltive™ SuperPulsed Laser System with the thulium fiber laser technology (thulium laser). The primary objective is to compare the procedural time (minutes). We will keep strict timing from the minute the ureteroscope is inserted into the patient to the time the ureteroscope has been removed. The following information will be collected as secondary outcomes: (1) stone free rate; (2) total operative time (minutes); (3) fragmentation/dusting time (minutes, total time to fragment the stone, including the laser was in use and time of pedal pauses); (4) lasing time (minutes, time the laser was in use, not including pedal pauses); (5) total energy used (kilojoules, kJ); (6) laser efficiency (mm per minute); (7) number of times the laser pedals are pressed (left, right, and total pedal presses); (8) stone analysis; (9) complications; (10) quality of life survey (WISQOL short form) both pre-operatively and post-operatively and (11) physician evaluation of the laser. Physicians will complete a one page survey at the end of the case evaluating the laser (survey included as attachment). A total of 3 clinic visits (i.e., pre-operative visit, the stone surgery, and one post-operative visit) will be needed for this study. Stone parameters (i.e. size, location, Hounsfield units, presence of hydronephrosis, stone volume), demographic information, co-morbidities, and post-operative parameters will be collected from the medical record.

Number of Participants

NCT04963062
Protocol 2021-0695

Approximately 164 patients will be enrolled (see Data Analysis for sample size justification).

Inclusion Criteria

1. Patients at least 18 years of age, and less than 89 years old.

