2. Patients with renal or ureteral urinary stones who require endoscopic treatment in the outpatient operating room
3. Patients' stone size in a single renal unit of 3-10 mm and 11-20 mm. Stone size is defined as the largest diameter of a single stone on pre-operative CT. Patients with multiple stones will be included as long as their largest stone size falls within the above parameters.

Exclusion Criteria

1. Patients under 18 years of age and over 89 years old.
2. Pregnant patients
3. Patients with transplant kidneys
4. Patients with irreversible coagulopathy
5. Patients with known ureteral stricture disease
6. Patient who do not have a pre-operative CT.
7. Non-English speaking, vulnerable patients such as lacking of decision-making capability, prisoner, adult unable to consent, will not be enrolled.

Recruitment methods

Patients who are to be scheduled for laser lithotripsy treatment of urinary stones as outpatients will be approached for study participation. During patients' pre-operative clinic visit, eligibility screening (by reviewing patients' medical record that is relevant for inclusion/exclusion criteria) will occur before recruitment. If patients meet the inclusion criteria, they will be initially approached by a study team member who also works in the urology clinic (i.e., the surgeon informs the patient that there's a research study they may be eligible for, and asked if they want to learn more about it).

No other recruitment materials will be used in this study. Holmium laser with Moses or thulium laser to treat stones is our routine care. Patients have been informed about the laser lithotripsy treatment before they schedule their surgery. We will only recruit patients from the outpatient OR, so this will not include patients who come in emergently through the Emergency Department.

NCT04963062
Protocol 2021-0695

No compensation will be provided to participants.

Consent Process

A study team member who is affiliated with the patient's clinical care (e.g., the surgeon) will initially approach the patients who are scheduled for laser lithotripsy treatment of urinary stones. (i.e., informed that there's a research study they may be eligible for, and asked if they want to learn more about it).

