If the patient is interested in the study, a member of the research team will approach him/her for enrollment. Consent process will be conducted face to face. Participants will be provided a written consent form in person. No waiting time is expected between informing the prospective participant and obtaining the consent.

Consent will take place during patients' pre-operative clinic visit. If patients are interested and there is not enough time to consent the patient in urology clinic, study information will be sent home with the patient and the patient will then be consented before their surgery in a private room (pre-operative room). Pre-operative room provides 1-1 1/2 hours of time. This should be ample time to conduct the consent process before surgery anesthesia.

All information about the study will be provided, and ample time will be made available for the participants to consider participation in the study.

Patient Randomization

Patients will be randomized (ratio 1:1) at the time of enrollment to be treated with either the holmium laser with Moses or the thulium laser. We will use Permuted Block Randomization (stratified by stone size 3 - 10 mm or 11-20 mm) (block size 4).

Study Procedures

1. The study team members review patients' medical record during patients' pre-operative clinic visit to see whether patients meet inclusion/exclusion criteria.
2. If patients meet the inclusion criteria, a study team member who is affiliated with the patient's clinical care (e.g., the surgeon) will initially approach the patients who are scheduled for laser lithotripsy treatment of urinary stones. (i.e., informed that there's a research study they may be eligible for, and asked if they want to learn more about it).
3. If the patient is interested in the study, a member of the research team will approach him/her for enrollment.
4. Patients will be asked to fill out a WISQOL short form at their pre-operative visit. This is standard of care for all stone patients in clinic.

5. Patients' total stone size (pre-operative CT) will be calculated and divided into two groups. Those with stones 3-10 mm and those with stones 11-20 mm. They will then be randomized to either the holmium laser with Moses or the thulium laser (randomization ratio 1:1) group.

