6. Patients will undergo stone surgeries with the laser that they are randomized to. A 200 micron fiber will be used with both machines. The patient's stone(s) will be treated in accordance with our routine clinical practice of fragmenting stone into small pieces (≤ 2 mm). One stone fragment will be collected for stone analysis if the patient does not already have a stone analysis on file (this is also standard of care). The faculty surgeons will perform all surgeries. We are unable to blind the surgeon to the laser used as the laser fibers and laser machines appear and sound different.
7. Procedural time as well as other information (see study design for the detail information) is collected.
8. After surgery, the patients will all have at least an abdominal x-ray within 1 month of surgery, if a CT scan has not already been completed(this is the standard of care). They will also be asked to fill out a WISQOL short form at their one-month follow up appointment. Otherwise, they will continue on our normal postoperative pathway. Postoperative complications will be collected.

Comparison of usual care and study procedures

Compared with our routine care, the only interventions imposed on subjects as a result of this study are (1) pre-procedural randomization to laser lithotripsy with either holmium laser with Moses or thulium laser, and (2) the use of patient & surgery information collected in describing our results. All the other activities are part of our routine clinical practice.

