Since we have 5 surgeons participating in this study, we will use university-based cloud service (such as OneDrive) to temporarily save the enrollment log. Study team member will use their Net ID to access the enrollment log. The enrollment log is completely deidentified. Only participant ID (such as 101, 102) and the laser each participant is randomized to are saved in the enrollment log. Once we complete data collection, we will permanently delete it from the cloud.

Share of results

NCT04963062
Protocol 2021-0695

Some of the information collected for this study will go in the patient's medical record. This includes the results of the one-month post-operative image, stone analysis, stone surgery, and all clinic visits information as these are being conducted as standard of care. All other information from research specific procedures will NOT go in the patient's medical records.

We only publish aggregated results. No individual results will be shared. We will not share the data with outside institutions.

Economic burden to participants

This study does not place financial burden to patients. The study interventions are our routine clinical practice to treat stones. It will be same as they are not involved in this study.

The cost of the two laser treatments are equivalent.

Data Analysis

The data collected will be analyzed as an intention-to-treat analysis. Statistical analyses will include T-test and, if appropriate, Chi-square tests (e.g., for categorical data), and two-way MANOVA. Patient demographics and stone characteristics will be summarized as appropriate as continuous variables (mean and standard deviation) or categorical variables (frequency, percentage). To compare the two groups, continuous variables such as procedural time, total OR time, WISQOL etc., will be analyzed using T test and two-way MANCOVA (stratified by stone size 3 - 10 mm or 11-20 mm). The surgeon will be controlled as a covariate. Categorical variables such as stone free rate will be analyzed using chi-square.

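### No allocation concealment is described, and a fixed block of 4 plus a shared log of past assignments lets the next laser be guessed about 65% of the time

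*Protocol*

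**What the plan says.** - **Scheme** (Protocol, Patient Randomization): "We will use Permuted Block Randomization (stratified by stone size 3 - 10 mm or 11-20 mm) (block size 4"). Timing is given in the same section: "Patients will be randomized (ratio 1:1) at the time of enrollment". Nothing says who generates or holds the list, or how an assignment reaches the person enrolling.
- **Log** (Protocol, Date Management and Confidentiality): "Only participant ID (such as 101, 102) and the laser each participant is randomized to are saved in the enrollment log". On access: "Study team member will use their Net ID to access the enrollment log". The reason given for cloud storage is that five surgeons take part. Stratum is not a listed field.
- **Who approaches patients** (Protocol, Consent Process): "A study team member who is affiliated with the patient's clinical care (e.g., the surgeon) will initially approach the patients". Study Procedures has study team members screen the records.
- **Timing of consent** (Protocol, Consent Process): "No waiting time is expected between informing the prospective participant and obtaining the consent", although consent may be deferred to the day of surgery.
- **Blinding** (Protocol, Study Procedures, step 6): "We are unable to blind the surgeon to the laser used".
- **Analysis.** Protocol, Data Analysis adjusts for surgeon and stratifies by stone size. The SAP's Data Analysis Plan compares procedural time with a Wilcoxon test and names no covariate. The SAP text available for this review does not mention randomization.

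**The concern.** Concealment prevents the choice of patient from depending on the laser that patient will get. Here, people who may decide whom to approach can see every earlier assignment, know the block size and know which laser they will be using. The Study Objectives also state an expectation that thulium will be faster. Someone who can guess the next laser may, without intending to, approach an easier case for one device and hold back a harder one. The resulting difference in procedural time would look like a device effect. The protocol's stated reason for randomizing is to reduce bias, and predictable allocation weakens that.

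**Working it through.** **The plan's own figures.** The documents give no figure for predictability. The benchmark is the sample size in Protocol, Data Analysis: difference 4.6 min, SD 6.5 min, two-sided 5% t-test, 33 per group. The exact t-test power is 0.796 at 32 and 0.808 at 33 per group, so 33 reproduces. Then 33 × 1.25 = 41.25, stated as 41, and 4 × 41 = 164.

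**Guess rate if each earlier patient's stratum is known.** A block of 4 has 6 possible orders. Guessing the arm used less so far in the block is correct with probability 1/2, 2/3, 2/3 and 1 at positions 1 to 4:

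(1/2 + 2/3 + 2/3 + 1)/4 = 0.708.

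The next assignment is certain at position 4 always and at position 3 one time in three: (0 + 0 + 1/3 + 1)/4 = 1/3. Over 82 patients per stratum, with the last block incomplete, the guess rate is 0.705.

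**Guess rate from the log as described (stratum absent).** At a random point in a stratum, the within-block imbalance is 0 with probability 5/12, +1 or −1 with probability 1/4 each, and +2 or −2 with probability 1/24 each. The log shows only the sum over the two strata. The reader guesses the laser with the smaller total.

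- Next patient's stratum is at ±1 (probability 1/2): the lagging arm comes next with probability 5/6, a gain of 1/3 over chance. The pooled total points the right way rather than the wrong way with net probability 5/12 + 1/4 = 2/3.
- Next patient's stratum is at ±2 (probability 1/12): the lagging arm is certain, a gain of 1/2. The pooled total points the right way with probability 23/24 and otherwise ties.

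Correct = 0.5 + (1/2)(1/3)(2/3) + (1/12)(1/2)(23/24) = 0.5 + 0.111 + 0.040 = **0.651**.

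Simulating 164 patients gives 0.65, and this barely moves for stratum splits from 50:50 to 80:20. About 2% of assignments are certain from the log alone.

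**Stale log** (simulated):

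| Enrolments between reading and assignment | Log only | Stratum known |
|---|---|---|
| 0 | 0.649 | 0.705 |
| 1 | 0.608 | 0.644 |
| 2 | 0.577 | 0.603 |
| 5 | 0.522 | 0.533 |

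**From guess to bias (steering assumed).** Suppose expected time is shifted by −s or +s minutes according to the guess, with no shift at ties. If p is the proportion of correct guesses, the arms differ by 4(p − 0.5)s. Per minute of s this is 4 × 0.150 = 0.60 (log only) and 4 × 0.205 = 0.82 (stratum known).

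| s (min) | Bias, every guess acted on | Bias, half acted on |
|---|---|---|
| 1 | 0.60 to 0.82 | 0.30 to 0.41 |
| 2 | 1.20 to 1.64 | 0.60 to 0.82 |
| 3 | 1.80 to 2.46 | 0.90 to 1.23 |

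**False-positive rate with no true difference.** With 82 per laser, SE = 6.5 × √(2/82) = 1.015 min. At s = 2 with half the guesses acted on, the bias is 0.60/1.015 = 0.59 or 0.82/1.015 = 0.81 standard errors. By the normal approximation the two-sided 5% test then rejects about 9% or 13% of the time. Simulated t-tests give about 8 to 9% and 12 to 13%. At s = 1 the rate is about 6 to 7%.

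**Effect of each remedy on the guess rate** (simulated):

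| Change | Log only | Stratum known |
|---|---|---|
| None | 0.650 | 0.705 |
| Blocks of 4, 6 and 8, log still open | 0.626 | 0.678 |
| Log closed, each surgeon knows only their own patients | 0.51 to 0.52 | not applicable |

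With varying blocks and stratum known, certain assignments fall from 33% to about 2%.

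**The case against.** The strongest reply is that silence is not absence. A concealed list may exist, and the log holds past assignments, not future ones. The access sentence also does not say that every recruiter reads every row, or that rows are in order of enrolment. The 65% needs a current log and someone who tallies it before approaching a patient. Steering would mean skipping or delaying eligible patients, which the protocol nowhere describes. Stone-size category is a stratification factor, so steering on it cannot unbalance the arms. Finally, the minutes of steering have no source in the documents.

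Much of this is fair as a limit on the claim. Concealment is *undescribed*, which is all that can be said, and part of the SAP was not available for this review. The lag table shows how fast the advantage fades, and the bias figures are illustrations.

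The point still stands. The fixed block size and the shared log are both written into the protocol, and together they make assignments predictable even if the list itself is locked away. The five-surgeon rationale makes surgeons the natural users of the log. With no waiting time expected before consent and randomization at enrollment, a guess made at approach will usually be current. Adjustment could use surgeon and the recorded features ("Stone parameters (i.e. size, location, Hounsfield units, presence of hydronephrosis, stone volume", among others). It would reduce bias acting through those features, but not through case difficulty that nobody records.

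**Conclusion.** The concern holds. No concealment step is described, and the published block of 4 with an open cumulative log lets a reader guess the next laser about 65% of the time, or about 71% if earlier strata are known from another source. This assumes that recruiters can open the log, that assignments can be read in order, and that no one else enrols in the meantime. The effect on the result rests on assumed steering. At 2 minutes either way on every guess, the bias would be 1.2 to 1.6 min, or 26% to 36% of the 4.6 min design difference (1.20/4.6 and 1.64/4.6); acting on half the guesses halves it. This is a weakness that should be corrected, not evidence that the result is biased.

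**What to change.** In this order:

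1. **Date Management and Confidentiality.** Restrict the cumulative log to a team member who neither recruits nor operates. This does most of the work. The guess rate falls to about 52% if each surgeon knows only their own patients; that is a best case, since colleagues in one department may talk.
2. **Patient Randomization.** State that each assignment is released for that patient alone, after consent, eligibility and stone-size stratum have been recorded and locked. Say who generates and holds the list.
3. **Block sizes.** Replace the fixed 4 with undisclosed, randomly varying sizes within each stratum, known only to whoever generates the list. On its own this is not enough: with the log open the guess falls only from 65% to 63%, or from 71% to 68% with stratum known.

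The cost is a change of file permissions, a regenerated list and two short protocol edits. Someone outside recruitment must be available to release assignments, including when consent is taken on the day of surgery. Arm imbalance at the end of each stratum may be slightly larger.

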We plan to enroll 164 patients in this study. Patients will be stratified into two groups according to their stone size (3-10 mm or 11-20 mm) and then randomized to either holmium laser with Moses or thulium laser. The stone size is defined as the largest stone size (largest diameter on pre-operative CT), if patients have multiple stones. Previous literature suggested stone size is associated with operative time.^{ix} A significance level of 0.05 will be used with a two-sided two-sample equal-variance t-test. Group sample sizes of 33 and 33 achieve 80% power to detect a significant difference between the means when the mean difference is 4.6 minutes with a standard deviation of 6.5 minutes. We also decide to increase the sample size by 25% (41 patients per group). This will allow for the possibility that the randomization scheme is intra-operatively abandoned for some reason (e.g., equipment failure), that the planned procedure was unable to be completed for some reason, as determined by the surgeon in

charge of the case, and/or that the patient – after his/her procedure – wishes to withdraw from the study and exclude his/her information from our analysis.

ⁱ Scales CD Jr, Smith AC, Hanley JM, Saigal CS; Urologic Diseases in America Project. Prevalence of kidney stones in the United States. *Eur Urol*. 2012 Jul;62(1):160-5.

ⁱⁱ Geraghty RM, Jones P, Somani BK. Worldwide Trends of Urinary Stone Disease Treatment Over the Last Two Decades: A Systematic Review. *J Endourol* 2017 Jun;31(6):547-556.

ⁱⁱⁱ Assimos D, Krambeck A, Miller NL, et al: Surgical Management of Stones: American Urological Association/Endourological Society Guideline, PART II. *J. Urol.* 2016.

^{iv} Andreeva V, Vinarov A, Yaroslavsky I, et al. Preclinical comparison of superpulse thulium fiber laser and a holmium:YAG laser for lithotripsy. *World J Urol*. 2020 Feb;38(2):497-503.

^v Ventimiglia E, Doizi S, Kovalenko A, et al. Effect of temporal pulse shape on urinary stone phantom retropulsion rate and ablation efficiency using holmium:YAG and super-pulse thulium fibre lasers. *BJU Int*. 2020 Jul;126(1):159-167.

^{vi} Bagrodia A, Gupta A, Raman JD, et al. Predictors of cost and clinical outcomes of percutaneous nephrolithotomy. *J Urol*. 2009 Aug;182(2):586-90.

^{vii} Schuster TG, Hollenbeck BK, Faerber GJ, Wolf JS Jr. Complications of ureteroscopy: analysis of predictive factors. *J Urol*. 2001 Aug;166(2):538-40.

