### **Data Analysis Plan**

Statistical analyses include using appropriate categorical/continuous and parametric/non-parametric statistical test. Patient demographics (such age, gender, race ethnicity) and stone characteristics (such as stone volume, location, density) will be summarized as appropriate as continuous variables (mean and standard deviation) or categorical variables (frequency, percentage). To compare the two groups, procedural time, laser time, ablation speed, ablation efficiency, total energy used, are analyzed using Wilcoxon test. The score of quality of life survey and laser evaluation survey are analyzed using MANOVA. Complication rate is analyzed using chi-square. Statistical significance is set as two-tailed p value < 0.05 and data are analyzed using SPSS 25.

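### The only planned analysis of procedural time with stone size and surgeon in it is a MANCOVA listed jointly with WISQOL, which may drop recorded times and does not test time itself

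*Protocol*

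**What the plan says.** Procedural time is the primary outcome (Protocol, Study Objectives and Research Design and Methods). It is timed in the operating room, from insertion to removal of the ureteroscope.

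The protocol's Data Analysis section states that "continuous variables such as procedural time, total OR time, WISQOL etc., will be analyzed using T test and two-way MANCOVA". The MANCOVA is stratified by the two stone-size bands, and "The surgeon will be controlled as a covariate". The section does not say which method is primary, which outcomes form the multivariate set, or how missing values are handled. It also states: "The data collected will be analyzed as an intention-to-treat analysis".

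On sample size, the same section says: "A significance level of 0.05 will be used with a two-sided two-sample equal-variance t-test".

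The post-operative questionnaire comes later. Study Procedures, step 8, says of patients: "They will also be asked to fill out a WISQOL short form at their one-month follow up appointment".

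The SAP's Data Analysis Plan assigns procedural time to a Wilcoxon test, with no mention of stone size or surgeon. It uses a multivariate method only for the surveys: "The score of quality of life survey and laser evaluation survey are analyzed using MANOVA".

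**The concern.** A MANCOVA has several dependent variables, and the only ones the protocol names are procedural time, total OR time and WISQOL. Fitting them jointly has two consequences.

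- **Loss of cases.** A standard MANCOVA uses only patients complete on every outcome. A patient whose time was recorded in surgery drops out if the one-month form is missing. If non-return is related to how the operation went, the adjusted comparison of times could also be biased.
- **A different question.** The omnibus test asks whether the arms differ on any outcome or combination of outcomes. The hypothesis, and the sample size, concern a difference in minutes on one outcome.

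Stone size is the randomisation stratum and the basis of the secondary objective, and surgeon is the one covariate the protocol says it will control. Only the MANCOVA is stated to contain them, so the adjusted analysis is the one exposed to both problems.

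**Working it through.** **Inputs from the Protocol, Data Analysis.** Difference 4.6 min, SD 6.5 min, two-sided alpha 0.05, 33 per group raised to 41, total 164. The standardised difference is d = 4.6/6.5 = 0.708, so d² = 0.501.

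**Assumptions, not in the documents.** 20% of one-month forms missing (10% and 30% also shown); three outcomes in the MANCOVA; an effect on procedural time only. Surgeon and the stone-size factor are ignored in the power formulas, and the same SD is used within and across strata.

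**1. The plan's own figure.** Power of the t-test comes from the noncentral t with 2n − 2 degrees of freedom and noncentrality d√(n/2). At n = 33 the noncentrality is 0.708 × √16.5 = 2.87 and power is 80.8%. The smallest n reaching 80% is 33. Then 33 × 1.25 = 41.25, stated as 41, and 4 × 41 = 164. The sample size reproduces.

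**2. Loss of cases alone, still testing procedural time by itself.** Group sizes are rounded down, for example 41 × 0.8 = 32.8, taken as 32.

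| WISQOL missing | n per group, one stratum | Power | n per arm, pooled | Power |
|---|---|---|---|---|
| 0% | 41 | 88.6% | 82 | 99.5% |
| 10% | 36 | 84.2% | 73 | 98.9% |
| 20% | 32 | 79.6% | 65 | 98.0% |
| 30% | 28 | 73.9% | 57 | 96.3% |

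**3. The omnibus test.** For two groups and p outcomes this is Hotelling's T², with power from a noncentral F on p and 2n − p − 1 degrees of freedom and noncentrality λ = nD²/2.

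- Uncorrelated outcomes: D² = d² = 0.501. At n = 41 and p = 3, λ = 20.5 × 0.501 = 10.27 and power is 75.0%. With 20% missing (n = 32) it is 62.3%.
- All correlations 0.5: D² = d² × (1 + 0.5)/[(1 − 0.5)(1 + 2 × 0.5)] = 0.501 × 1.5 = 0.751. At n = 41, λ = 15.40 and power is 91.0%, slightly above the univariate 88.6%.
- Pooled, uncorrelated: 97.5% at 82 per arm with complete data, and 93.1% at 65 per arm with 20% missing.

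**4. Does a significant omnibus result speak to time?** Suppose there is no effect on procedural time and a 0.5 SD effect on one of the two other outcomes, uncorrelated. Then D² = 0.25, and at 82 per arm λ = 41 × 0.25 = 10.25. The three-outcome test is significant in 76% of trials. The same calculation at 41 per group gives λ = 5.125 and 43%.

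**The case against.** The strongest reply is that the primary comparison is already safe.

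- The protocol's sentence keeps a t-test beside the MANCOVA, the sample size rests on a t-test, and the SAP uses a Wilcoxon test for procedural time. None of these needs a WISQOL form. This stands. A reader might infer that the MANCOVA replaces the primary question; the documents do not support that, since nothing makes it primary.
- The list is introduced as examples and left open, so it does not define a joint outcome set. This also stands: joint fitting is an inference from the choice of a multivariate method.
- A model with stone size as a factor pools both strata, where the power loss is small. This is correct, and it confines the loss mainly to comparisons within a stratum.
- Adding outcomes need not cost power. At correlation 0.5 it does not, and two times measured on the same operation are unlikely to be uncorrelated.

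Four further inferences go too far.

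- **Intention-to-treat.** The Safety Monitoring Plan uses the term for laser switches, that is, analysis as randomised. Dropping incomplete cases is better described as an unaddressed missing-data problem than as a direct contradiction.
- **Complete primary data.** The protocol itself expects procedures that cannot be completed and patients who withdraw their data, so procedural time is not guaranteed for everyone.
- **Pedal counts.** Total presses alongside left and right would make the model singular, but nothing says that all three enter it.
- **The SAP surveys.** The SAP does not model procedural time with WISQOL. Whether the patient and surgeon surveys share one MANOVA is not stated.

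What remains is that neither univariate test is stated to include stone size or surgeon. The reply protects an unadjusted comparison and leaves the adjusted one exposed.

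**Conclusion.** The point holds for the adjusted analysis of procedural time, conditional on a joint fit. The only planned model with the stratum and surgeon would then omit patients whose time is known, and its omnibus p-value would not answer the question in minutes.

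The power cost is moderate within a stone-size stratum and small over the whole trial. It depends on an assumed rate of missing forms, on which outcomes are included and on their correlations; WISQOL is routine at both visits, so the true missing rate may be low. The mismatch between test and question does not depend on missing data. There is no arithmetic error in the sample size. The change is worth making because a better-matched analysis is available from the same data at almost no cost.

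**What to change.** In both the Protocol's Data Analysis section and the SAP, name one univariate linear model as the analysis of procedural time. It should include:

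- laser and stone-size band;
- the laser-by-size interaction, for the secondary objective;
- surgeon as a categorical factor.

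Fit it to all randomised patients with a recorded time, analysed as randomised, and report the difference in minutes with its confidence interval. Keep the Wilcoxon test as a sensitivity analysis, so that the two documents agree.

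Analyse WISQOL, the surgeon's laser evaluation and each other outcome in its own model, on the patients who have that outcome.

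The cost is an edit to two sections and a few more separate models to report. No new data or software is needed.
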